7.2. Subject Exclusion Criteria

- Subject should be excluded if they apply to any of the following criteria.
- 283 1) Cardiogenic shock
- 284 2) Active internal bleeding, bleeding diathesis, or coagulopathy
- 285 3) Gastrointestinal bleeding or genitourinary bleeding, hemoptysis, or vitreous hemorrhage within 286 2 months
- 287 4) Major surgery within 6 weeks
- History of intracranial bleeding, intracranial neoplasm, intracranial arteriovenous malformation, or intracranial aneurysm
- 290 6) Anemia (hemoglobin < 10 g/dL) or platelet count of less than 100,000/mm³ at the time of screening
- 292 7) Concomitant treatment with oral anticoagulant agent (vitamin-K antagonists or novel oral anticoagulants such as dabigatran, rivaroxaban, apixaban, or edoxaban)
- 294 8) Daily treatment with non-steroidal anti-inflammatory drugs (NSAIDs) or cyclooxygenase-2 295 inhibitors
- 296 9) Malignancy or life expectancy of less than one year
- 297 10) Moderate or severe hepatic dysfunction (Child Pugh B or C)

- 298 11) Symptomatic patients with sinus bradycardia (sick sinus syndrome) or atrioventricular (AV)
 299 block (AV block grade II or III, bradycardia-induced syncope; except for patients implanted with
 300 permanent pacemaker)
- 301 12) Symptomatic patients with chronic obstructive pulmonary disease (Medical research council grade ≥3)
- 13) Intolerance of or allergy to aspirin, ticagrelor or clopidogrel
- 14) Subjects who are under renal replacement therapy due to end-stage renal disease or who have history of kidney transplantation
- 306 15) Galactose intolerance, lactase insufficiency or glucose-galactose malabsorption
- 16) Subjects who are actively participating in another clinical trial with 3 months of randomization (except for observational study)
- 309 **17)** Pregnant and/or lactating women
- 310 18) Subjects considered unsuitable for this study by the investigator

7.3. Study Population

7.3.1. Sample Size

311312

313

314315

316

317

318

319

320

321322

323

324

325

326327

328

	Test	Control	Total Sample Size
No. of efficacy case	1165	1165	2330
Including follow-up loss rate (10%)	1295	1295	2590

7.3.2. Sample Size Estimation

The present study is designed to show noninferiority of the treatment group with aspirin plus clopidogrel versus the control group with aspirin plus ticagrelor. Sample size is based on the combined occurrence rate of ischemic and bleeding events between 1 and 12 months after AMI. According to the PLATO investigators, the event rate of primary efficacy endpoint including CV death, MI or stroke was 5.28% in the ticagrelor group and 6.60% in the clopidogrel group between 1 and 12 months after the index event². In the meantime, since there were no reported data on the bleeding event rate associated with ticagrelor from 1 to 12months after AMI, especially BARC bleeding rate at the time of the present study design, we assumed the event rate of BARC 2, 3 and 5 bleeding from the event rates of non-CABG related PLATO major or minor bleeding during a year of ticagrelor therapy (8.7%) and non-CABG related major bleeding of first 30 days (2.47%) and after 30 days (2.17%) in the PLATO trial. For the event rate of BARC 2, 3 and 5 bleeding associated with clopidogrel from 1 to 12 months after AMI, the event rate was assumed from the event rates of non-CABG related PLATO major or minor bleeding during a year of clopidogrel therapy (7.0%) and non-CABG related PLATO major or minor bleeding during a year of clopidogrel therapy (7.0%) and non-CABG related PLATO major or minor bleeding during a year of clopidogrel therapy (7.0%) and non-CABG related PLATO major or minor bleeding during a year of clopidogrel therapy (7.0%) and non-

329 CABG related major bleeding of first 30 days (2.21%) and after 30 days (1.65%) in the clopidogrel 330 group of the PLATO trial⁷. We applied mathematical formula for the estimation of the event rate of 331 BARC 2, 3, 5 bleeding from the event rates of non-CABG related PLATO major or minor bleeding: 332 "In the ticagrelor group 333 non-CABG major bleeding first 30 days: non-CABG major bleeding after 30days = 2.47: 2.17 334 non-CABG total bleeding first 30 days : non-CABG total bleeding after 30 days = $(8.7- \chi)$: χ 335 $2.47:2.17 = (8.7- \chi): \chi$ $\chi = 4.07\%$ 336 337 In the clopidogrel group 338 non-CABG major bleeding first 30 dasy: non-CABG major bleeding after 30 days = 2.21:1.65 339 non-CABG total bleeding first 30 days : non-CABG total bleeding after 30 days = $(7.0-\gamma)$: χ

340 $2.21:1.65 = (7.0-\chi):\chi$ 341 $\chi = 2.99\%$ "

After applying mathematical formula, the estimated BARC 2, 3 and 5 bleeding would be 4.07% in the ticagrelor group and 2.99% in the clopidogrel group. Thus, the expected event rate of the primary endpoint from 1 to12 months after index PCI was 9.35% (ischemic event of 5.28% + bleeding event of 4.07%) in the ticagrelor group and 9.59% (ischemic event of 6.6% + bleeding event of 2.99%) in the clopidogrel group. We chose the noninferiority margin in accordance with clinical judgment and other relevant studies with a noninferiority design at the present study design. The noninferiority margin of two contemporary trials of antiplatelet treatment after PCI that were available up to that time was equivalent to a 40% increase in the expected event rate^{18, 19}. The steering committee decided that the noninferiority margin in our study should be less than a 40% increase compared to the expected event rate of the control group. After considering clinically acceptable relevance and the feasibility of study recruitment, we finally selected the noninferiority margin of 3.0%, which was equivalent to a 32% increase in the expected event rate. Sample size calculations (PASS 13, NCSS, LLC, Kaysville, Utah, USA) were performed based on one-sided α of 0.05 and a power of 80 %. To achieve these goals, a total of 2,230 patients were needed. After considering a follow-up loss rate of 10%, a total of 2,590 (1,295 patients in each group) patients were required.

357358359

342343

344

345

346

347

348

349350

351

352

353

354

355

356

8. Study Duration

360 IRB approval to Dec. 31st, 2020

361

[figure not shown]
362

[figure not shown]
9. Study Method

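### The 80% power rests on an unstated assumption of no true difference; at the plan's own expected rates of 9.35% and 9.59%, 1,165 per arm give 73.6% at one-sided 0.05

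*Protocol*

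**What the plan says.** Protocol section 7.3.2 builds an expected primary-endpoint rate for each arm by adding an ischemic and a bleeding component. For the control arm it gives "9.35% (ischemic event of 5.28% + bleeding event of 4.07%) in the ticagrelor group". The test arm's figure, built the same way, is "9.59% (ischemic event of 6.6% + bleeding event of 2.99%) in the clopidogrel group". It then fixes the margin: "we finally selected the noninferiority margin of 3.0%, which was equivalent to a 32% increase in the expected event rate". The sample size calculations "were performed based on one-sided α of 0.05 and a power of 80" per cent. SAP section 8.1 repeats these rates, the margin, the alpha and the power.

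The table in section 7.3.1 reads "No. of efficacy case 1165 1165 2330", raised to 1,295 per arm and 2,590 in total for 10% loss to follow-up. Neither document says which event rates went into the software, or that the arms were taken as equal.

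**The concern.** The margin applies to clopidogrel minus ticagrelor, and the events are harmful. An expected difference of 9.59 − 9.35 = +0.24 points therefore shortens the distance to the margin from 3.00 to 2.76 points, a loss of 8%. Non-inferiority sample sizes are sensitive to this, because the required number varies with the inverse square of that distance.

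The clopidogrel rate is not incidental: it has its own derivation in section 7.3.2 and is half of what the section calls the expected event rate. A reader will take 80% to be the power at those two rates. If it is not, the plan understates the chance of failing to show non-inferiority under its own assumptions.

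**Working it through.** **Inputs** (protocol sections 7.3.1 and 7.3.2; SAP section 8.1): pC = 0.0935, pT = 0.0959, margin 0.03, one-sided alpha 0.05, power 0.80, 1:1 allocation, 10% loss.

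**Formulas** (difference of proportions, unpooled normal approximation):

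- n per arm = (z₁₋α + z₁₋β)² × [pC(1−pC) + pT(1−pT)] / [0.03 − (pT−pC)]², with (1.645 + 0.842)² = 6.1826 from unrounded z values.
- Power = Φ{[0.03 − (pT−pC)]/SE − z₁₋α}, with SE = √{[pC(1−pC) + pT(1−pT)]/n}.

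**Step 1: reproduce the plan's figure.** Put 9.35% in both arms. The variance sum is 2 × 0.0935 × 0.9065 = 0.16952, and n = 6.1826 × 0.16952/0.0009 = 1,164.5, so 1,165. Then 1,165/0.9 = 1,294.4, so 1,295 per arm and 2,590 in total. Every figure in the section 7.3.1 table is recovered, and power at 1,165 is 80.0%.

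**Step 2: use the plan's two expected rates.** The variance sum is 0.08476 + 0.08670 = 0.17146, and n = 6.1826 × 0.17146/0.0276² = 1,391.6, so 1,392 per arm (2,784 in total). After 10% loss this is 1,392/0.9, so 1,547 per arm (3,094 in total).

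**Step 3: power at those rates, one-sided 0.05.**

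- 1,165 per arm: SE = 0.01213; 0.0276/0.01213 = 2.275; Φ(2.275 − 1.645) = 73.6%.
- 1,295 per arm, all fully observed: SE = 0.01151; 0.0276/0.01151 = 2.399; Φ(2.399 − 1.645) = 77.5%.

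**Step 4: could another formula explain 1,165 at 9.35% and 9.59%?** None tried does so:

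| Variant at the stated rates | n per arm |
|---|---|
| Difference with the wrong sign | 1,010 |
| Pooled variance | 1,392 |
| Farrington-Manning | 1,406 |
| Continuity correction | 1,464 |
| Null variance at pC and pC + margin | 1,507 |
| One-sided 0.025 | 1,767 |

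Farrington-Manning power at 1,165 is 73.2%.

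**Step 5: what drives the result.** Equal rates of 9.59% give 1,192 per arm and 79.2% power at 1,165. The zero difference matters far more than the level.

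**Step 6: alpha.** Protocol section 14.3.1 and SAP section 8.3 state a one-sided 0.05 test but also judge non-inferiority by the upper limit of a two-sided 95% confidence interval, which is one-sided 0.025.

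| 1,165 per arm | One-sided 0.05 | Two-sided 95% interval |
|---|---|---|
| 9.35% in both arms | 80.0% | 70.1% |
| 9.35% vs 9.59% | 73.6% | 62.4% |

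**The case against.** **Sizing at zero difference from the control rate is a common convention**, and section 7.3.2 expresses its margin relative to the control rate (3.0/9.35 = 32%). This stands. A reader might infer that the calculation is invalid or that the trial must grow to 3,094. The documents do not support that: the convention is legitimate, and only its disclosure is missing.

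**The 80% does not depend on exactly 9.35%.** It would be too strong to say that it holds only at that common rate, since Step 5 gives 79.2% at a common 9.59%. The value 9.35% matters only because it reproduces 1,165 exactly.

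**A flat type II error of 26.4% would be too strong.** The primary analysis uses Kaplan-Meier estimates with censoring, so patients lost later contribute partial follow-up. With 1,295 randomized per arm and the planned 10% loss, power at the stated rates lies between 73.6% and 77.5%, a type II error of 22.5% to 26.4%.

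**The rates are themselves sums.** A patient with both an ischemic and a bleeding event counts once in the composite, so 9.35% and 9.59% are upper bounds, and the gap depends on an overlap that is not given. This argues against false precision but does not remove the shortfall. As an illustration, assume that the components are independent. The overlaps are then 0.0528 × 0.0407 = 0.21 and 0.066 × 0.0299 = 0.20 points, the rates 9.14% and 9.39%, and power at 1,165 is 73.8%.

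**The alpha conflict costs more power than this point does.** True: about 10 to 11 points against 6.4. It is a separate contradiction, but no corrected power statement is safe until it is settled.

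**Conclusion.** The point holds as an unstated assumption that leaves the power statement wrong as written. The sample size is reproduced exactly with 9.35% in both arms, while the same section presents 9.35% and 9.59% as the expected rates. At those rates, a 3-point margin and one-sided alpha 0.05, power is 73.6% with the planned 1,165 evaluable per arm. That is 6.4 points below the stated 80% and equivalent to 1,392 − 1,165 = 227 evaluable patients per arm. If all 1,295 per arm were fully observed it would be 77.5%, still short.

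That equal rates were entered is inferred from the exact match, since the software inputs are not given. The figures rest on the normal approximation and take the summed rates at face value.

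The point is separate from the conflict between the table's 2,330 and the text ("a total of 2,230 patients were needed"). Correcting the text to 2,330 leaves power at 73.6%; taking 2,230 literally (1,115 per arm) gives 71.9%. Type I error, the margin, the endpoint and the analysis sets are unaffected.

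**What to change.** Enrol no more patients on this account. In protocol section 7.3.2 and SAP section 8.1, state the equal-rate assumption and give the power at the expected rates beside it. If one-sided 0.05 governs, the sentence could read: *The sample size of 1,165 evaluable patients per arm assumes a true event rate of 9.35% in both arms, which gives 80% power at one-sided alpha 0.05; at the expected rates of 9.35% (ticagrelor) and 9.59% (clopidogrel) the power is about 74%.*

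First settle which criterion decides non-inferiority in protocol section 14.3.1 and SAP section 8.3. If the two-sided 95% confidence interval rule is kept, the same sentence must carry one-sided alpha 0.025 with 70.1% and 62.4% instead. The section 7.3.1 table states no power and needs no change for this point.

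The cost is one sentence in each document and a less favourable stated power.

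### The 1,165 per arm gives 80% power only if the two arms have equal true rates; at the protocol's own 9.59% vs 9.35% power is about 74% at one-sided 0.05 and 62% under the 95% CI rule

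*Protocol*

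**What the plan says.** Protocol 7.3.2 builds the expected rates of the primary endpoint from ischemic and bleeding components. For the control arm it gives "9.35% (ischemic event of 5.28% + bleeding event of 4.07%) in the ticagrelor group". The figure for the test arm, built the same way, is "9.59% (ischemic event of 6.6% + bleeding event of 2.99%) in the clopidogrel group". The expected disadvantage for clopidogrel is therefore 0.24 percentage points. On the margin it says: "we finally selected the noninferiority margin of 3.0%, which was equivalent to a 32% increase in the expected event rate". The calculation itself is reported as using "one-sided α of 0.05 and a power of 80 %. To achieve these goals, a total of 2,230 patients were needed", and the total then rises to 2,590 once 10% loss to follow-up is allowed for.

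The table in 7.3.1, in the row "No. of efficacy case", gives 1,165 per arm and 2,330 in total, then 1,295 per arm and 2,590 with loss. SAP 8.1 repeats the rates, alpha, power and the 2,230.

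Protocol 14.3.1 and SAP 8.3 declare non-inferiority when the upper limit of a two-sided 95% confidence interval for the risk difference (clopidogrel minus ticagrelor) is below 3%. The same sections also describe a one-sided test at 0.05 and treat the two rules as equivalent.

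**The concern.** Section 7.3.2 goes to some length to derive unequal rates and says the sample size rests on them. A reader will therefore take 80% as the power at 9.59% vs 9.35%. The tabulated size appears instead to come from a true difference of zero, which is not stated anywhere.

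The sizing alpha (one-sided 0.05) is also looser than the interval rule for the decision (a two-sided 95% interval, equivalent to one-sided 0.025). Finally, the text total and the table total disagree.

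The interpretation of a failed non-inferiority test is at stake. At a true 80% power, the chance of missing non-inferiority under the planning assumptions is one in five. Under the plan's own rates it is higher, so a negative result would be given more weight than it deserves.

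**Working it through.** **Inputs (protocol 7.3.1, 7.3.2 and 14.3.1).** pC = 0.0935 (ticagrelor), pT = 0.0959 (clopidogrel), margin 0.03, power 80%, 1:1 allocation, 10% loss. Sizing alpha is one-sided 0.05; the 95% interval rule is one-sided 0.025.

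The component figures check: 8.7 × 2.17/(2.47 + 2.17) = 4.07; 7.0 × 1.65/(2.21 + 1.65) = 2.99; 3.0/9.35 = 32%.

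**Formula (unpooled normal approximation).**

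n per arm = (z_alpha + z_beta)² × [pT(1 − pT) + pC(1 − pC)] / [0.03 − (pT − pC)]²

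**Step 1: reproduce the plan's figure.** With 0.0935 in both arms and one-sided 0.05:

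(1.645 + 0.842)² × 0.1695 / 0.03² = 1,164.5, so 1,165 per arm.

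1,165/0.9 = 1,294.4, so 1,295 per arm and 2,590 in total. This matches the table exactly.

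**Step 2: use the stated rates.** The variance sum is 0.08670 + 0.08476 = 0.17146, and the distance to the margin is 0.03 − 0.0024 = 0.0276.

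- One-sided 0.05: 1,391.6, so 1,392 per arm; with 10% loss 1,547 per arm, 3,094 in total.
- One-sided 0.025: 1,766.7, so 1,767 per arm; with 10% loss 1,964 per arm, 3,928 in total.

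The choice of formula does not close the gap. At one-sided 0.05 and the stated rates, pooled variance gives 1,392, Farrington-Manning 1,406, a continuity correction 1,464 and null-rate variance 1,506. Reversing the sign of the difference gives 1,010.

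**Step 3: power of the planned size.** Power = Φ(0.0276/SE − z_alpha) at the stated rates, with SE = √(0.17146/n).

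- n = 1,165: SE = 0.01213. Φ(2.275 − 1.645) = 73.6%; Φ(2.275 − 1.960) = 62.4%.
- n = 1,295: SE = 0.01151. Φ(2.399 − 1.645) = 77.5%; Φ(2.399 − 1.960) = 67.0%.

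| True rates (clopidogrel vs ticagrelor) | n per arm | One-sided 0.05 | 95% CI rule |
|---|---|---|---|
| 9.35% vs 9.35% | 1,165 | 80.0% | 70.1% |
| 9.59% vs 9.35% | 1,165 | 73.6% | 62.4% |
| 9.59% vs 9.35% | 1,295 | 77.5% | 67.0% |
| 9.59% vs 9.35% | 1,115 (half of 2,230) | 71.9% | 60.5% |

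A binomial simulation with 1,000,000 runs at 1,165 per arm and the stated rates gave 73.7% and 62.5%. Farrington-Manning gave 73.2% and 61.8%.

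**Step 4: the total.** 2,330/0.9 = 2,589, which becomes 2,590 once each arm is rounded up. 2,230/0.9 = 2,478. Only 2,330 is consistent with the enrolment target.

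**The case against.** The arithmetic is not in dispute. The case on the other side concerns framing and weight.

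- **The 62% combines two separate problems.** Leaving out the 0.24-point difference takes power from 80.0% to 73.6%. The further fall to 62.4% comes from deciding by the 95% interval, while 14.3.1 also describes a one-sided test at 0.05. This is fair, and 62% should always be quoted as conditional on the interval rule. Power is nevertheless below 80% at the stated rates under either rule. The two rules are not equivalent, since one-sided 0.05 corresponds to a 90% interval.
- **Kaplan-Meier estimation uses patients until they are censored.** The effective size then lies between 1,165 and 1,295 per arm, and the shortfall at one-sided 0.05 is 2.5 to 6.4 points. This also stands, and is why both ends are reported.
- **Assuming no true difference is a common convention in non-inferiority designs.** It is legitimate if stated. Here it is unstated, and the text presents unequal rates as the basis.
- **Equal rates of 9.35% are not the only near match.** Equal rates of 9.59% give 79.2% power and need 1,192 per arm. Only 9.35% in both arms gives 1,165 exactly, and in either case the expected difference was left out.
- **The 2,230 looks like a one-digit slip.** That is likely, but it stands in both documents and contradicts the table.

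**Conclusion.** The concern holds. The 1,165 per arm follows from equal true rates of 9.35% at one-sided 0.05, and not from the rates that 7.3.2 presents. At 9.59% vs 9.35%, power is 73.6% to 77.5% at one-sided 0.05 and 62.4% to 67.0% under the two-sided 95% interval. In each range the lower figure is for 1,165 per arm and the upper for 1,295 fully contributing. The corresponding chance of missing non-inferiority is about 23% to 26%, or 33% to 38%, against the 20% implied. Even with equal rates, 1,165 per arm gives only 70.1% under the interval rule.

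These figures rest on the protocol's own rates and margin and on a normal approximation to the risk difference, supported by simulation. The zero-difference input is inferred from the exact match, because the protocol does not list the rates entered in the software. The shortfall does not raise the risk of a false non-inferiority claim. It does make the stated power wrong, and the stated total contradictory, for the primary endpoint.

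**What to change.** Keep 2,590 and correct the statement in protocol 7.3.2 and SAP 8.1:

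1. Change 2,230 to 2,330.
2. State that 1,165 per arm assumes equal true rates of 9.35% and one-sided alpha 0.05, after checking this against the record of the original calculation.
3. Add the power at the expected rates (9.59% vs 9.35%) under the 95% interval criterion: about 62% with 1,165 per arm and 67% if all 1,295 per arm contribute. If the one-sided 0.05 test is confirmed as the governing rule instead, the figures to report are about 74% and 77%.

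The cost is wording in two sections and a less favourable power statement. No patients are added, and the margin and analysis do not change.

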9.1. Study Process

364 Phase IV

9.2. Study Design

Screening period

To conduct screening AMI patients based on the inclusion/exclusion criteria who (1) have been treated with ticagrelor + aspirin for at least 30±7 days after an index PCI, (2) received full explanation of the study details, (3) given written consent.

To randomize eligible subjects within 30±7 days after AMI undergoing PCI with newer ge neration DES, and receiving aspirin and ticagrelor to the treatment and control groups in a 1:1 ratio.

Treatment period

Enrolled patients receive clopidogrel 75mg + aspirin 100 mg (treatment group) or ticagrelor 90mg bid +aspirin 100mg treatment (control group) for 11 months (post-AMI 1 month to 12 months) and evaluation safety and efficacy by conducting physical examination, checking vital sign, and collecting adverse events at post-PCI 3M, 6M, 12M visits.

Laboratory and imaging tests, which undergo according to the medical judgment of each investigator during the study period, are collected by reviewing medical records or EMR.

9.3. Randomization

9.3.1. Subject Assignment and Randomization

Randomization will be performed to ensure the scientific validity of the clinical test. This will maximize the comparability of the test and control group and eliminate the subjectivity of the researchers in subject group assignment. Before PCI, a 250-325mg loading dose of aspirin is given to patients who are naïve to treatment and all patients receive a loading dose of ticagrelor 180mg. Discharge medication consists of aspirin 100mg once and ticagrelor 90mg twice per day. All patients receive treatment with aspirin plus ticagrelor for 1 month after the index PCI (screening period). At 30 ± 7days after index PCI, eligible patients were randomly assigned either to the 1) aspirin 100 mg plus clopidogrel 75mg daily (treatment group) or 2) aspirin 100 mg plus ticagrelor 90mg twice daily (control group) in a 1:1 ratio. Randomization will occur centrally. To randomize a patient, the investigative site will enter the subject into the designated electronic system and obtain the treatment assignment (clopidogrel + aspirin or ticagrelor + aspirin) in a 1:1 ratio. At 1 month visit after AMI, eligible subjects were assigned to each treatment group following an access to the interactive web-based response system (IWRS, Medical Excellence Inc., Seoul, Korea) by the investigator or designee. Randomization sequence was created by an independent statistician using SAS 9.3 (SAS Institute Inc. Cary, NC, USA) statistical software and was stratified by study center and type of AMI (STEMI or NSTEMI) and with a 1:1 allocation using hidden random block size.

404 405 406

407

408

409

410

411

412

413

389

390 391

392

393

394

395

396

397

398

399

400

401

402

403

